3 GLOSSARY OF TERMS AND ABBREVIATIONS

Abbreviation	Description
Аβ	amyloid beta
AD	Alzheimer's disease
ADAS-Cog	Alzheimer's Disease Assessment Scale – cognition subscale
AE	adverse event
ADCS-ADL	Alzheimer's Disease Cooperative Study – Activities of Daily Living
ADCS-CGIC	Alzheimer's Disease Cooperative Study – Clinical Global Impression of Change
AKI	Acute kidney injury
ALT	alanine aminotransferase
APOE	gene which codes for apolipoprotein E
AST	aspartate aminotransferase
AUC	area under the concentration-time curve
β-HCG	beta human chorionic gonadotropin
BACE	beta secretase cleaving enzyme
BP	systolic and diastolic blood pressure
BUN	blood urea nitrogen
С	Celsius
CFT	Category Fluency Test
C _{max}	maximum concentration
CNS	central nervous system
COWAT	Controlled Word Association Test
CSF	cerebrospinal fluid

Abbreviation	Description
C _{ss}	steady state concentration
C-SSRS	Columbia Suicide Severity Rating Scale
dL	deciliter
DSMB	Data Safety Monitoring Board
ECG	electrocardiogram
EOS	End of Study
F	Fahrenheit
FBR	Future Biomedical Research
FDA	Food and Drug Administration
GCP	Good Clinical Practice
GDS	Geriatric Depression Scale
GFR	glomerular filtration rate
GMP	Good Manufacturing Practice
h	hour(s)
HBsAg	hepatitis B surface antigen
HCV	hepatitis C virus
hERG	human Ether-à-go-go Related Gene
Hgb	hemoglobin
HIV	human immunodeficiency virus
IC50	half maximal inhibitory concentration
ICF	Informed Consent Form
ICH	International Conference on Harmonization
IRB	Institutional Review Board
IRT	Interactive Response Technology

Abbreviation	Description
IVRS / IWRS	Interactive Voice Response Systems / Interactive Web Response Systems
kg	kilogram
KIM-1	kidney injury molecule -1
LP	lumbar puncture
MAD	multiple ascending dose
MCI	mild cognitive impairment
μg	microgram
mg	milligram
mL	milliliter
mmol	millimolar
MMSE	Mini Mental State Exam
MRI	Magnetic Resonance Imaging
MTD	maximum tolerated dose
NAG	N-acetyl-beta-D-glucosaminidase (an indicator of renal damage)
NIH	National Institutes of Health
NIA	National Institute on Aging
NTB	Neuropsychological Test Battery
PD	pharmacodynamics
PK	pharmacokinetic
QD	once daily
SAE	serious adverse event
t _{1/2}	terminal half life
TFF3	trefoil factor 3 (an indicator of renal damage)

Abbreviation	Description
TK	toxicokinetic
T _{max}	time to maximum concentration
ULN	upper limit of normal
Vd	volume of distribution

4 INTRODUCTION

4.1 Background

Synaptic dysfunction and loss caused by age-dependent accumulation of synaptotoxic beta-amyloid ($A\beta$) 1-42 oligomers is proposed to underlie cognitive decline in Alzheimer's Disease (AD). Accumulation of $A\beta$ protein leads to self-association, resulting in formation of oligomers. Cognition Therapeutics Inc. has demonstrated that $A\beta$ oligomers bind saturably to a single, high affinity site on the surface of neuronal synapses (Izzo et al 2014a; Izzo et al., 2014b). Once bound, these oligomers alter membrane trafficking rate and reduce surface expression of neuronal receptors critical for synaptic plasticity (Hsieh 2006, Lacor 2007). This leads to failure of long-term potentiation, reversible spine loss in neurons, and impaired cognitive performance that progresses throughout the course of AD (Shankar 2007, Zempel 2013). Cognition Therapeutics Inc. has identified a receptor not previously associated with AD that mediates the binding of $A\beta$ oligomers to neurons, the sigma-2/PGRMC1 receptor (Izzo et al 2014a, b).

Cognition Therapeutics has discovered a series of highly brain penetrant, novel sigma-2/PGRMC1 antagonist molecules, including CT1812 that both prevent and competitively displace oligomer binding to neuronal synapses, prevent spine loss in neurons and prevent and treat oligomer-induced deficits in membrane trafficking *in vitro*. These antagonists displace endogenous human AD patient oligomers from brain tissue sections in a dose-dependent manner. Chronic administration of sigma-2/PGRMC1 antagonists at doses that reach brain concentrations corresponding to greater than 80% estimated receptor occupancy at the sigma-2/PGRMC1 receptor restore cognitive function in aged transgenic hAPP Swe/Ldn mice models of AD. These molecules work by allosteric antagonism of the sigma-2/PGRMC1 receptor protein, or a protein closely associated with it, to modulate oligomer binding site affinity, representing a novel previously unrecognized mechanism of action for disease-modifying Alzheimer's therapeutics.

CT1812 is a highly brain penetrant novel sigma-2/PGRMC1 antagonist molecule that prevents and displaces binding of A β 42 oligomers to receptors on brain cells. In vitro, in cultured rat neurons, CT1812 not only antagonizes binding of A β 42 oligomers, but also prevents A β oligomerinduced membrane trafficking changes. Chronic treatment with this first-in-class, highly brain-penetrant, disease-modifying oligomer receptor antagonist restores aged AD model transgenic mouse performance to normal in multiple cognitive tests. Sponsor hypothesizes that chronic treatment with CT1812 could restore neuronal plasticity compromised by A β oligomers, and thus improve cognitive function in patients throughout the course of AD. This approach is

fundamentally different than that of other therapeutics in development (such as beta secretase cleaving enzyme [BACE] inhibitors) that focus on lowering the brain concentrations of beta amyloid protein. This product could provide the first clinical test of the hypothesis that cognitive decline in AD is related to toxic effects of Aβ oligomers on synaptic function.

There are no currently approved products for the treatment of prodromal mild cognitive impairment (MCI) or established AD that function by blocking the binding and pathological activity of soluble Aβ oligomers. While there are some approved drugs for other indications that demonstrate significant affinity at sigma-2/PGRMC1 receptors, unlike CT1812, these other drugs have significant activity at other pharmacological targets besides the sigma-2/PGRMC-1 receptor, which would make them undesirable therapeutic agents for this indication. None of these have been tested or approved for treating AD or cognitive impairment.

Cognition Therapeutics, Inc. is developing this oral formulation of CT1812 to treat mild to moderate AD and early AD / mild cognitive impairment.

4.2 Nonclinical Experience

4.2.1 Nonclinical Pharmacology Studies

CT1812 is a lipophilic isoindoline formulated as a fumarate salt and is the result of a structure-based medicinal chemistry optimization program comprised of over 300 analogs. CT1812's properties are fully described along with all preclinical studies in the Investigator's Brochure. CT1812 has a high affinity at the target receptor sigma-2/PGRMC1 (S2) and is >100-fold selective for this receptor over other receptors and ion channels.

In vitro pharmacodynamic (PD) studies confirmed CT1812 target binding specificity, affinity, and engagement, including the prevention and reversal of A β oligomer binding and the prevention of A β oligomer-induced synapse loss.

In vivo PD studies confirmed the desired consequences of target engagement, including cognitive improvements in an aged transgenic mouse model of AD following oral administration of an apparently tolerated dose of CT1812 daily for 9 weeks. Additional *in vivo* PD studies, using an A β oligomer detecting microelectrode in an aged transgenic mouse model of AD, demonstrated that administration of CT1812 caused an acute increase in soluble A β oligomers in the interstitial fluid of the hippocampus and a sustained increased in soluble A β oligomers in the CSF of the lateral ventricle of the brain. These increases in soluble A β oligomers occurred without a change in the

amount of soluble A β 1-40, indicating that displacement of A β oligomers occurred following treatment with CT1812.

4.2.2 Nonclinical Pharmacokinetic Studies

Absorption of CT1812 following oral gavage administration to mice, rats and dogs appears to be very rapid, with brain concentrations exceeding those concurrently measured in plasma. The drug is highly protein-bound in plasma from rat, mouse, dog, and human, but only weakly bound to blood cells. Systemic exposures to CT1812 following oral administration to rats and dogs were greater than dose-proportional at high, toxicologically relevant dosages. Extensive first-pass metabolism appears to be via oxidation and/or direct glucuronidation.

Studies with human recombinant cytochrome P450 (CYP) isoforms show rapid metabolism ($t_{1/2}$ of 6.8 min) by CYP3A4, and slower metabolism ($t_{1/2}$ of 57 and 81 minutes) by CYP2D6 and CYP2C19. A direct glucuronide conjugate was also observed *in vitro* in human hepatocyte incubations, consistent with that observed *in vivo* in rats and dogs.

CT1812 was not an inhibitor of CYP1A2, CYP2B6, or CYP2C8, with less than 50% inhibition of activity observed at the highest concentration evaluated (10 μ M). CT1812 was a weak inhibitor of CYP2C9, CYP2C19, CYP2D6, and CYP3A4, with IC50 values ranging from 4.4 to 38 μ M. However, when evaluated in the context of systemic exposure data in humans, the drug-drug interaction liability from these effects was considered to be minimal. CT1812 was found to be an inducer of CYP3A4 (\geq 0.3 μ M), suggesting a potentially clinically significant risk of drug-drug interactions with this isoform, but induction of CYP2B6 and CYP1A2 appear less likely. CT1812 does appear to be a substrate for p-glycoprotein (P-gp) and inhibits P-gp with an IC50 of 10 μ M. This is considered to be potentially clinically significant, primarily due to the possibility of interactions in the gastrointestinal (GI) tract. *In vitro* inhibition of the OATP1B1 transporter (IC50 of 11.5 μ M) by CT1812 does not appear to be clinically relevant, when evaluated in the context of systemic exposure data in humans. As assessed per the FDA 2012 draft guidance for DDI evaluations, clinically relevant DDI are suggested via CT1812 effects on CYP3A4 and P-gp.

4.2.3 Nonclinical Safety Studies

Two hERG (human Ether-à-go-go Related Gene) assays were performed to assess effects of CT1812 on the rapidly activating delayed rectifier potassium channels (IKr) using channels stably transfected and over-expressed in Chinese Hamster Ovary cells. Using whole-cell patch clamp electrophysiology, CT1812 was tested in both studies in duplicate at concentrations of 1, 3, 10,

and 30 μ M. Mean IC₅₀ values of 26 μ M and 0.6 μ M were determined in the first and second assay, respectively. Reasons for the differing results are unknown. However, no ECG effects were noted in the telemeterized dog cardiovascular safety study or in the multiple-dose dog pivotal toxicology study when tested up to high-dose mean C_{max} values of approximately 4 μ M.

Safety pharmacology studies with rats revealed no apparent effects on CNS or pulmonary parameters following single oral dosages that exceeded the maximum tolerated dose in this species.

General toxicology studies with rats and dogs following oral dosing of CT1812 revealed dose-limiting toxicity that manifested as degenerative changes in the proximal tubules of kidney, hypercalcemia, and vascular mineralization and/or degeneration involving multiple tissues and organs in each species. Tolerable and intolerable dosages and exposures, characterized with each species, informed the selection of dosages for this trial.

Additionally, toxicology studies revealed several test article-related clinical laboratory changes, including elevated serum creatinine and/or BUN that correlated with mild weight loss, elevated serum calcium, and reduced urinary specific gravity. The exact mechanism for these changes cannot be determined from those studies. Serum and urine tests will be performed in this trial to evaluate the effect of study drug administration on renal function (including serum creatinine, serum calcium, urine calcium).

Genetic toxicology studies revealed no positive responses in bacterial and mammalian in vitro assays, or in an in vivo mouse bone marrow micronucleus assay when tested up to maximally feasible dosages.

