15.2 Number of Participants Chosen for This Study

For this trial groups of 48 active-dosed participants per dose level are felt to give adequate sensitivity to detect adverse events. A sample size of 48 active-dosed participants for each dose level (100 mg, 300 mg) has 91% power to detect at least 1 occurrence of any drug-related AE with a true prevalence in the treated population of 5%. Additional participants may be added to replace participants with significant disruption to their visit schedule due to COVID or if there are unanticipated dropouts.

Additionally, for the primary exploratory efficacy analysis relating to the ADAS-COG 11 comparing the combined CT1812 treatment groups versus the placebo group, 48 participants per group provides 81% power to show a treatment difference of 3.0 points assuming a two-sided test at the alpha=0.05 level of significance, a SD of 5.4 points, and a dropout rate of 15%.

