#### 9.4. Electrocardiograms

[figure not shown]
Descriptive summaries will be presented for ECG measures of PR interval (msec), RR interval (msec), QRS interval (msec), QT interval (msec), QTc interval (both Fredericia's and Bazett's correction methods), and HR. These summaries will be presented by visit and treatment group.

The frequency and percentage of participants with normal, clinically significant abnormal, and not clinically significant abnormal ECG results will be summarized for the Safety Population by treatment group and visit.

All ECG results will be listed.

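### SAP 9.4 has no count of participants by QTc level or by QTc rise, so prolongation in a few people would be hard to see by arm

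*Protocol*

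**What the plan says.** Protocol 4.2.3 gives hERG IC50 values of 26 and 0.6 µM that "were determined in the first and second assay, respectively", and comments: "Reasons for the differing results are unknown". The next sentence offers the in vivo evidence: "no ECG effects were noted in the telemeterized dog cardiovascular safety study", nor in the repeated-dose dog toxicology study, up to a mean Cmax of about 4 µM. Protocol 4.3 describes earlier human dosing without ECG or QTc results.

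ECG change is a listed safety endpoint (Protocol 6.2.1, SAP 2.2.1). SAP 9.4 plans three displays:

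- Descriptive statistics for PR, RR, QRS, QT, QTc (Fridericia and Bazett) and heart rate. "These summaries will be presented by visit and treatment group". Under SAP 4.1 these include the minimum and maximum.
- An overall reading: "The frequency and percentage of participants with normal, clinically significant abnormal, and not clinically significant abnormal ECG results will be summarized", by arm and visit.
- A listing: "All ECG results will be listed".

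Three other provisions bear on this:

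- SAP 6.1.6 keeps an early-termination visit before Day 170 out of the summary tables. Protocol 10.2.14 includes an ECG at that visit.
- SAP 9.2.1 counts ALT and AST at or above 3 times ULN and tabulates each participant's most extreme post-baseline laboratory shift.
- Protocol 15.4 plans descriptive changes from baseline for ECG intervals. SAP 9.4 does not repeat this, and SAP 10 does not list it as a change.

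**The concern.** Safety is the primary objective, and one of two hERG assays leaves a question that the protocol does not explain. The trial records machine-measured ECGs about 1 to 2 hours after dosing, when Protocol 4.3 places the plasma peak, so the data to examine QTc will exist.

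The planned displays suit an effect that shifts everyone slightly. They suit poorly an effect confined to a few participants. No display says how many people in each arm reached a given QTc, how many rose by a given amount from their own starting value, or what each person's worst on-treatment value was. The SAP does this for laboratory data, so the omission departs from its own practice. A participant who stops early loses the final ECG from both the maximum and the abnormal count.

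**Working it through.** **Inputs from the documents.** 48 participants per arm, 1:1:1 (Protocol 15.2, SAP 3.5), so 96 on active drug. IC50 values of 26 and 0.6 µM and dog Cmax of about 4 µM (Protocol 4.2.3). Scheduled post-dose ECGs on Days 1, 28, 56, 98 and 182: five (Protocol Table 1).

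**Assumed inputs.** The documents give no QTc cut-off, size of rise, number affected or SD. I take rises of 30 or 60 ms, 1 to 3 people affected, and an SD of QTc change of 10 to 20 ms.

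**The plan's own figure.** The chance of at least one event in 48 at 5% prevalence is 1 − 0.95^48 = 0.915, matching the stated 91%.

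**hERG comparison.** 26 / 0.6 = 43. The dog Cmax is 4 / 0.6 = 6.7 times the lower IC50 and 4 / 26 = 0.15 times the higher.

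**Shift of the arm mean** = (number affected × rise) / n.

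- 60 ms in 1, 2 or 3 of 48: 1.25, 2.5 or 3.75 ms. A 30 ms rise gives half of each.
- 60 ms in 3 of the 96 pooled: 180 / 96 = 1.9 ms.

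**Against sampling error.** SE of a 48 versus 48 difference = SD × √(2/48).

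| Assumed SD (ms) | SE (ms) | 95% half-width (ms) | 3.75 ms / SE |
|---|---|---|---|
| 10 | 2.04 | 4.0 | 1.8 |
| 15 | 3.06 | 6.0 | 1.2 |
| 20 | 4.08 | 8.0 | 0.9 |

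Across this range, 60 ms in three people lies within the noise of a comparison of means.

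**What a participant count would show.** If a share p of those treated truly qualify and each is captured, the chance of at least one is 1 − (1 − p)^n.

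- p = 5%: 91.5% in 48, 99.3% in 96.
- p = 2%: 62% in 48, 86% in 96.
- None observed: the one-sided 95% upper bound, 1 − 0.05^(1/n), is 6.1% for 48 and 3.1% for 96.

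**What it would show by chance.** Assume no drug effect and normally distributed changes with mean zero. A single rise above 30 ms has probability P(Z > 30/SD): 0.13%, 2.3% and 6.7% for SD 10, 15 and 20. For the worst of five ECGs, treated as independent, 1 − (1 − P)^5 gives 0.7%, 11% and 29%. A shared baseline makes the five changes positively correlated, so the true figures would be lower. Above 60 ms with SD 20, the worst-of-five figure is 0.7%.

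**Baseline.** SAP 6.1.1 takes the last value up to the first dose, and the SAP document history says the definition now includes the day of first dose. Protocol 10.2.2 places the Day 1 ECG after dosing. Read by clock time, the baseline is the screening ECG. Read by calendar day, an on-drug ECG could become the baseline and hide a rise.

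**The case against.** The strongest reply is that an affected participant would not go unseen. SAP 9.4 counts abnormal ECGs by arm and lists every result, and summaries carry the maximum. A clinically significant finding can be an adverse event, which SAP 9.1 counts per participant. The medical monitor reviews safety data every two weeks and the DSMB quarterly. All of this stands, so a reader who infers that such a case would disappear goes further than the documents allow. These routes are still weak. The maximum is one observed value per visit, with no count and no link to that person's pre-dose level. The abnormal reading is not defined in terms of QTc. The listing compares nothing between arms.

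If the change-from-baseline summary of Protocol 15.4 were restored, its maximum would show the largest individual rise at each visit. That would help, but it would still not give the number affected.

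Three stronger inferences are tempting and not supported:

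- **That the dog studies are uninformative because of protein binding.** Protocol 4.2.2 does say "The drug is highly protein-bound in plasma from rat, mouse, dog, and human". If 4 µM is total drug, the free level reaches 0.6 µM only with a free fraction of at least 0.6 / 4 = 15%. The documents give no bound fraction, do not say whether 4 µM is total or free, and refer to the Investigator's Brochure for detail. The 0.6 µM value also lies below the lowest concentration tested (1 µM), which makes it less certain in either direction.
- **That the sample-size rationale requires QTc counts.** The sentence that 48 per dose "has 91% power to detect at least 1 occurrence of any drug-related AE with a true prevalence in the treated population of 5" per cent concerns adverse events, which are already counted per participant.
- **That a threshold table would prove an effect.** Three of 48 against 0 of 48 gives a two-sided Fisher p of 2 × C(48,3)/C(96,3) = 0.24. The table's value is description, not power.

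**Conclusion.** The gap is real and of moderate weight. SAP 9.4 contains no participant-level count by QTc level, by QTc rise or by worst on-treatment value, and ECGs from early-termination visits before Day 170 are listed only. The unexplained hERG difference is a reason to look at individuals; it is not evidence that CT1812 prolongs QT, and the negative dog studies count on the other side. The silence of the protocol on clinical QTc does not mean that no such data exist elsewhere.

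The absence of the counts and the treatment of early-termination ECGs rest on the documents alone. The size does not: the 3.75 ms shift, and its ratio of 0.9 to 1.8 to its standard error, depend on the assumed 60 ms, 3 of 48 and SD of 10 to 20 ms. The consequence is that an imbalance between arms in the number of people with prolonged QTc could be recorded without being tabulated. This is a worthwhile low-cost improvement, not a flaw that invalidates the safety analysis.

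**What to change.** Add one descriptive table to SAP 9.4 for the Safety Population, with columns for placebo, 100 mg, 300 mg and pooled CT1812.

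- Count each participant once, at the worst QTcF after the first dose, including unscheduled and early-termination ECGs. Protocol 9.5.1 allows the early-termination visit up to 2 weeks after the last dose, so footnote the time since last dose for those ECGs.
- Prespecify categories of absolute level and of rise from baseline, for example above 450, 480 and 500 ms and above 30 and 60 ms. These examples do not come from the documents. They are reporting categories for the sponsor to confirm and carry no consequence for dosing.
- State that the ECG baseline is the pre-dose screening ECG and that the Day 1 post-dose ECG cannot serve as baseline.
- Flag the counted participants in the ECG listing.
- State that the table is descriptive, is read against placebo and carries no test.

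The cost is one table and a line of definition, from interval data already collected. The drawback is that isolated exceedances from noise will appear, on placebo too, mostly in the lower rise category; the placebo column shows how many to expect.

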4.3 Clinical Experience

CT1812 has been administered safely with good tolerability in over 60 healthy volunteers in a placebo-controlled Phase 1a trial (COG 0101). Six single (10-1120 mg) and three multiple dose cohorts (QD, 14 days, 280-840 mg) were observed under close inpatient stay (N=6-8 treated, 2 placebo per cohort). Plasma concentrations of drug were shown to be approximately dose proportional across two orders of magnitude [0.13-14.93 mg (free base equivalent)/kg], and accumulation was minimal. Peak concentrations of CT1812 were reached within 1 to 2 hours and the plasma half-life was shown to be approximately 12 hours. Adverse events were mostly mild to moderate in severity and principally included headache, nausea, vomiting, diarrhea, constipation, abdominal pain, dyspepsia, upper respiratory tract infection, lightheadedness, syncope, myalgia, dizziness, rash, and pain at the lumbar puncture site in those participants who

had lumbar punctures. There was only one AE of severe intensity, being an SAE of upper respiratory tract infection, occurring in one participant in the 840 mg dose of the MAD study, believed to be unrelated to study drug based on a similar pattern of URTIs in subjects receiving drugs other than CT1812 in the study unit during the same time period. One participant in the multiple dose cohort study developed a rash while on study drug. This participant showed improvement after discontinuing CT1812.

No evidence of renal toxicity or hypercalcemia has been observed based on routine measures of renal function (serum creatinine, BUN) or cystatin C.

Four participants in the MAD study showed an increase in liver function tests below 3X the upper limit of normal (including one participant on placebo). Subsequent studies will closely monitor liver enzyme parameters to determine if these were sporadic findings or possibly drug-related.

A fed cohort (280 mg) single dose was compared to the fasting cohort of 280 mg and no significant food effect was observed. A multiple dose cohort of elderly (≥65 years old) healthy volunteers was dosed at 560 mg x 14 days, and their exposures were similar to the 840 mg younger healthy volunteer participants.

In COG0103, 15 healthy volunteers evaluated potential effects of CT1812 on the disposition of sensitive substrates of selected CYP isoenzymes CYP2C19 (omeprazole), CYP2C9 (tolbutamide), CYP2D6 (dextromethorphan), and CYP3A4/5 (midazolam). Participants were administered the probe drugs on Day -2 and PK evaluations performed. On Days 1 through 6, each participant took CT1812 560 mg. The CT1812 dose on Day 6 was taken concomitantly with the probe drug cocktail, and PK evaluation was conducted. No significant interaction was observed for isoenzymes 2C19 and 2C9. A weak drug interaction was observed between steadystate CT1812 and midazolam 4 mg (CYP3A4). Midazolam AUC_{last} and the AUC_{last} ratio (parent to metabolite) decreased by 24% and 28%, respectively, when midazolam 4 mg was taken with steady state CT1812 than when midazolam was taken alone. A weak drug interaction was observed between steady-state CT1812 and dextromethorphan 50 mg (CYP2D6), as indicated by a 1.75-fold and 2-fold increase in dextromethorphan AUC_{last} and C_{max}, respectively, following the combination treatment relative dextromethorphan alone: to however. dextromethorphan/dextrorphan AUClast ratio was similar between treatments. Based on the small magnitude of the interactions observed in this study for the isoenzymes CYP2D6 and CYP3A4, clinically meaningful implications are unlikely.

A Phase 1a/2 trial (COG0102) evaluated the safety and pharmacokinetics of three doses of oncea-day CT1812 (90 mg, 280 mg, 560 mg) dosed for 28 days in participants with mild to moderate Alzheimer's disease. This study enrolled 19 participants in a 1:1:1:1 ratio of these doses vs. placebo. In general, all doses were relatively well tolerated, with no SAEs. All AEs were considered mild or moderate. While there was an increased frequency observed in total AEs with increasing dose, the small number of treated participants does not permit definitive conclusions regarding the incidence of AEs by dose in a larger study population. Specific AEs which were noted to occur with greater frequency at the 560 mg dose included transient lymphocytopenia, nausea, vomiting, headache, fatigue, and depression. These AEs resolved in most instances while treatment was ongoing; one participant at the 560 mg dose experienced an ALT increase of 4.7 X ULN which resolved to normal levels after discontinuation of study drug. Cognitive outcomes were similar across the treatment groups. Plasma CT1812 concentration increased approximately dose proportionally, with a dose dependent increase in CSF concentration. CSF concentrations at all tested doses were > 80% of estimated brain PGRMC-1 receptor occupancy, which was the threshold associated with efficacy in preclinical studies.

For additional information about the clinical study program, please refer to the current Investigator Brochure.

